### Sampling Times for Pharmacodynamic, and Safety Assessments for the Extension Study Period

Study Period		PD			Safety		
Ext Week	Ext Day	B-cell Kinetics	CRP, ESR	RF, anti-CCP	Immuno-globulin	Immuno-genicity	Hematology, Clinical Chemistry, Urinalysis
0	0	Predose  ; end of infusion  ; 1 hour after end of infusion 	Pretreatment 	Pretreatment 	Pretreatment 	Pretreatment 	Pretreatment 
2	14	Pretreatment 	NA	NA	NA	NA	Pretreatment 
8	56	Time not specified 	Time not specified 	NA	Time not specified 	Time not specified 	Time not specified 
16	112	Time not specified 	Time not specified 	NA	Time not specified 	Time not specified 	Time not specified 
24	168	Time not specified 	Time not specified 	Time not specified 	Time not specified 	Time not specified 	Time not specified 
EOS 		Time not specified 	Time not specified 	Time not specified 	Time not specified 	Time not specified 	Time not specified 

Abbreviations: anti-CCP, anti-cyclic citrullinated peptide; CRP, C-reactive protein; EOS, end of study; ESR, erythrocyte sedimentation rate; NA, not applicable; PD, pharmacodynamic; RF, rheumatoid factor.

1. Predose: Blood samples will be obtained within 15 minutes prior to the beginning of the study drug infusion.
2. End of infusion: Blood samples will be obtained within 15 minutes after the end of study drug infusion.
3. 1 hour after end of infusion: Blood samples will be obtained 1 hour ( $\pm 15$  minutes) after the end of study drug infusion on dosing days.
4. Pretreatment: Blood samples will be obtained prior to the study drug infusion.
5. Time not specified: Blood samples will be obtained any time during the day.
6. The EOS Visit only needs to be completed if the patient withdraws prior to study completion. End-of-study assessments should be completed at least 8 weeks after the last study drug infusion and before Extension Week 24 if a patient withdraws prior to the completion of Extension Week 24 visit. If the patient has completed the Study Period, a separate EOS Visit is not required. In this case, the last visit will be considered the EOS Visit.

**APPENDIX 2: Table of CTCAE Terms and Grades**

CTCAE Term	Laboratory Parameter	Level	Grade 1	Grade 2	Grade 3	Grade 4
Anemia	Hemoglobin	Low	<LLN - 10.0 g/dL; <LLN - 100 g/L	<10.0 - 8.0 g/dL; <100 - 80g/L	<8.0 g/dL; <80 g/L;	-
Alanine aminotransferase increased	Alanine Aminotransferase (ALT)	High	>ULN - 3.0 x ULN	>3.0 - 5.0 x ULN	>5.0 - 20.0 x ULN	>20.0 x ULN
Alkaline phosphatase increased	Alkaline phosphatase	High	>ULN - 2.5 x ULN	>2.5 - 5.0 x ULN	>5.0 - 20.0 x ULN	>20.0 x ULN
Aspartate aminotransferase increased	Aspartate Aminotransferase (AST)	High	>ULN - 3.0 x ULN	>3.0 - 5.0 x ULN	>5.0 - 20.0 x ULN	>20.0 x ULN
Blood bilirubin increased	Total Bilirubin	High	>ULN - 1.5 x ULN	>1.5 - 3.0 x ULN	>3.0 - 10.0 x ULN	>10.0 x ULN
Chronic kidney disease	Creatinine Clearance (Est by Weight)	Low	<LLN - 60 ml/min	<60 - 30 ml/min	<30 - 15 ml/min	<15 ml/min

CPK increased	Creatine Phosphokinase (CPK)	High	>ULN - 2.5 x ULN	>2.5 x ULN - 5 x ULN	>5 x ULN - 10 x ULN	>10 x ULN
Creatinine increased	Creatinine	High	>1 - 1.5 x baseline; >ULN - 1.5 x ULN	>1.5 - 3.0 x baseline; >1.5 - 3.0 x ULN	>3.0 baseline; >3.0 - 6.0 x ULN	>6.0 x ULN
GGT increased	Gamma Glutamyl Transferase	High	>ULN - 2.5 x ULN	>2.5 - 5.0 x ULN	>5.0 - 20.0 x ULN	>20.0 x ULN
Hemoglobin increased	Hemoglobin	High	Increase in >0 - 2 gm/dL above ULN or above baseline if baseline is above ULN	Increase in >2 - 4 gm/dL above ULN or above baseline if baseline is above ULN	Increase in >4 gm/dL above ULN or above baseline if baseline is above ULN	-
Hypercalcemia	Calcium	High	>ULN - 11.5 mg/dL; >ULN - 2.9 mmol/L	>11.5 - 12.5 mg/dL; >2.9 - 3.1 mmol/L	>12.5 - 13.5 mg/dL; >3.1 - 3.4 mmol/L	>13.5 mg/dL; >3.4 mmol/L
Hyperkalemia	Potassium	High	>ULN - 5.5 mmol/L	>5.5 - 6.0 mmol/L	>6.0 - 7.0 mmol/L	>7.0 mmol/L

Hypernatremia	Sodium	High	>ULN - 150 mmol/L	>150 - 155 mmol/L	>155 - 160 mmol/L;	>160 mmol/L
Hypoalbuminemia	Albumin	Low	<LLN - 3 g/dL; <LLN - 30 g/L	<3 - 2 g/dL; <30 - 20 g/L	<2 g/dL; <20 g/L	-
Hypocalcemia	Calcium	Low	<LLN - 8.0 mg/dL; <LLN - 2.0 mmol/L	<8.0 - 7.0 mg/dL; <2.0 - 1.75 mmol/L	<7.0 - 6.0 mg/dL; <1.75 - 1.5 mmol/L	<6.0 mg/dL; <1.5 mmol/L
Hypoglycemia	Glucose	Low	<LLN - 55 mg/dL; <LLN - 3.0 mmol/L	<55 - 40 mg/dL; <3.0 - 2.2 mmol/L	<40 - 30 mg/dL; <2.2 - 1.7 mmol/L	<30 mg/dL; <1.7 mmol/L
Hypokalemia	Potassium	Low	<LLN - 3.0 mmol/L	<LLN - 3.0 mmol/L	<3.0 - 2.5 mmol/L	<2.5 mmol/L
Hyponatremia	Sodium	Low	<LLN - 130 mmol/L		<130 - 120 mmol/L	<120 mmol/L
Lymphocyte count decreased	Lymphocytes	Low	<LLN - 800/mm  ; <LLN - 0.8 x	<800 - 500/mm  ; <0.8 - 0.5 x 10e  /L	<500 - 200/mm  ; <0.5 - 0.2 x 10e 	<200/mm  ; <0.2 x 10e  /L

			10  /L		/L	
Lymphocyte count increased	Lymphocytes	High	-	>4000/mm  - 20,000/mm 	>20,000/mm 	-
Neutrophil count decreased	Total Neutrophils	Low	<LLN - 1500/mm  ; <LLN - 1.5 x 10  /L	<1500 - 1000/mm  ; <1.5 - 1.0 x 10  /L	<1000 - 500/mm  ; <1.0 - 0.5 x 10  /L	<500/mm  ; <0.5 x 10  /L
Platelet count decreased	Platelet count	Low	<LLN - 75,000/mm  ; <LLN - 75.0 x 10  /L	<75,000 - 50,000/mm  ; <75.0 - 50.0 x 10  /L	<50,000 - 25,000/mm  ; <50.0 - 25.0 x 10  /L	<25,000/mm  ; <25.0 x 10  /L
White blood cell decreased	White Blood Cells	Low	<LLN - 3000/mm  ; <LLN - 3.0 x 10  /L	<3000 - 2000/mm  ; <3.0 - 2.0 x 10  /L	<2000 - 1000/mm  ; <2.0 - 1.0 x 10  /L	<1000/mm  ; <1.0 x 10  /L

Note: The LLN and ULN values will be the normal ranges as provided by the central laboratory at each relevant transfer.

### APPENDIX 3: Rule of combining Preferred Terms

AESOC	AEPT	Combined PT
Gastrointestinal disorders	Abdominal pain	Abdominal pain
	Abdominal pain lower	
	Abdominal pain upper	
Infections and infestations	Abscess oral	Abscess
	Subcutaneous abscess	
Blood and lymphatic system disorders	Anaemia	Anaemia
	Iron deficiency anaemia	
Psychiatric disorders	Anxiety	Anxiety
	Anxiety disorder	
Musculoskeletal and connective tissue disorders	Arthritis reactive	Arthritis
	Arthritis	
Infections and infestations	Bacterial vaginosis	Bacterial vaginosis
	Vaginitis bacterial	
Infections and infestations	Asymptomatic bacteriuria	Bacteriuria
	Bacteriuria	
Cardiac disorders	Bradycardia	Bradycardia
	Sinus bradycardia	
Cardiac disorders	Cardiac failure	Cardiac failure
	Cardiac failure chronic	
General disorders and administration site conditions	Chest pain	Chest pain
	Non-cardiac chest pain	
Hepatobiliary disorders	Bile duct stone	Cholelithiasis
	Cholelithiasis	
Infections and infestations	Conjunctivitis	Conjunctivitis

	Conjunctivitis bacterial	
Respiratory, thoracic and mediastinal disorders	Cough Productive cough	Cough
Skin and subcutaneous tissue disorders	Dermatitis Dermatitis allergic Dermatitis atopic Dermatitis contact Seborrhoeic dermatitis Solar dermatitis	Dermatitis
Metabolism and nutrition disorders	Diabetes mellitus Type 2 diabetes mellitus	Diabetes mellitus
Skin and subcutaneous tissue disorders	Drug eruption Toxic skin eruption	Drug eruption
Skin and subcutaneous tissue disorders	Dyshidrotic eczema Eczema Eczema nummular	Eczema
Injury, poisoning and procedural complications	Ankle fracture Facial bones fracture Femur fracture Foot fracture Hand fracture Humerus fracture Lower limb fracture Lumbar vertebral fracture Rib fracture Tibia fracture Ulna fracture	Fracture

	Wrist fracture	
Infections and infestations	Fungal infection Fungal skin infection Genital infection fungal Oral candidiasis Oral fungal infection Vulvovaginal candidiasis	Fungal infection
Nervous system disorders	Headache Tension headache	Headache
Infections and infestations	Helicobacter gastritis Helicobacter infection	Helicobacter infection
Infections and infestations	Herpes simplex Herpes zoster Oral herpes	Herpes virus infection
Metabolism and nutrition disorders	Glucose tolerance impaired Hyperglycaemia Impaired fasting glucose	Hyperglycaemia
Immune system disorders	Drug hypersensitivity Hypersensitivity	Hypersensitivity
General disorders and administration site conditions	Catheter site pain Injection site haematoma Injection site pain Puncture site pain	Injection site reaction
Injury, poisoning and procedural complications	Chest injury Craniocerebral injury Concussion Contusion	Injury

	
 
Eye contusion
 
Fall
 
Injury
 
Limb injury
 
Meniscus injury
 
Skin injury
 
Tendon rupture
 
Wound
 
	
Musculoskeletal and connective tissue disorders	
 
Intervertebral disc disorder
 
Intervertebral disc protrusion
 
	Intervertebral disc disorder
Infections and infestations	
 
Bacterial infection
 
Localised infection
 
Pulpitis dental
 
Skin infection
 
Tooth infection
 
Eczema infected
 
	Localised infection
Infections and infestations	
 
Bronchiolitis
 
Bronchitis
 
Lower respiratory tract infection
 
Lung infection
 
Respiratory tract infection
 
Respiratory tract infection viral
 
	Lower respiratory tract infection
Nervous system disorders	
 
Neuropathy peripheral
 
Peripheral sensory neuropathy
 
Toxic neuropathy
 
	Neuropathy peripheral
General disorders and administration site conditions	
 
Face oedema
 
Generalised oedema
 
	Oedema

	Localised oedema Oedema peripheral Peripheral swelling	
Infections and infestations	Otitis externa Otitis media Otitis media acute Otosalpingitis	Otitis
Infections and infestations	Pneumocystis jirovecii pneumonia Pneumonia	Pneumonia
Skin and subcutaneous tissue disorders	Pruritus Pruritus generalised	Pruritus
Skin and subcutaneous tissue disorders	Rash Rash erythematous Rash generalised Rash macular Rash maculo-papular Rash pruritic	Rash
Infections and infestations	Rhinitis Viral rhinitis	Rhinitis
Infections and infestations	Acute sinusitis Sinusitis	Sinusitis
Gastrointestinal disorders	Mouth ulceration Stomatitis	Stomatitis
Cardiac disorders	Sinus tachycardia Supraventricular tachycardia Tachycardia Ventricular tachycardia	Tachycardia

Infections and infestations	Body tinea Tinea capitis Tinea infection Tinea pedis	Tinea infection
Infections and infestations	Laryngitis Nasopharyngitis Pharyngitis Pharyngitis bacterial Pharyngotonsillitis Tonsillitis Tracheitis Tracheobronchitis Upper respiratory tract infection Viral upper respiratory tract infection	Upper respiratory tract infection
Infections and infestations	Cystitis Urinary tract infection	Urinary Tract Infection
Skin and subcutaneous tissue disorders	Mechanical urticaria Urticaria	Urticaria
Vascular disorders	Venous thrombosis Venous thrombosis limb	Venous thrombosis
Ear and labyrinth disorders	Vertigo Vertigo positional	Vertigo

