7.8.4.2 Adverse Events

Adverse events will be coded to system organ class (SOC) and preferred term (PT) according to MedDRA. Adverse events will be graded for severity according to the CTCAE v4.0.

The following AE summaries will be reported by SOC, PT, and treatment:

- Number and percentage of patients reporting at least 1 AE
- Number and percentage of patients reporting at least 1 SAE
- Number and percentage of patients discontinuing the study drug due to an AE
- Number and percentage of patients with AEs of special interest (infusion-related AEs and infections)

If more than 1 AE is recorded for a patient within any SOC or PT, the patient will be counted only once within the respective summary.

Adverse events will also be summarized by maximum intensity and relationship to study drug with the percentage of patients in each category. If more than 1 AE is recorded for a patient within any SOC or PT, the patient will only be counted once using the most severe assessment.

Adverse events of special interest will also be summarized by intensity.

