### 13. Safety Analyses

The safety analyses will be performed on the safety population and safety – Extension Study Period subset by treatment group presenting data on hypersensitivity monitoring via vital sign measurements (including blood pressure, heart and respiratory rates, and temperature) and electrocardiograms (ECG), immunogenicity tests, vital sign measurements, ECGs, signs and symptoms of tuberculosis (TB), physical examination findings, adverse events (AEs), infections, Infusion-Related Reactions (IRRs), malignancy, clinical laboratory results (hematology, clinical chemistry, urinalysis, and immunoglobulins), and pregnancy tests. Combined PTs using the [APPENDIX 3: Rule of combining Preferred Terms](#) will be summarized in AE tables. Listings will include the PTs as coded without applying the PT combining rule.

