#### **13.1.4.1. Infections**

Infections are considered AEs of special interest and include but are not limited to serious, including fatal, bacterial including tuberculosis, fungal, and new or reactivated viral infections. New or reactivated viral infections include cytomegalovirus, herpes simplex virus, parvovirus B19, varicella zoster virus, West Nile virus, and hepatitis B and C. Infections are coded with a SOC of “Infections and infestations”.

Treatment-emergent infections will be summarized by relationship, intensity, SOC, and PT for the safety population and safety – Extension Study Period subset, displaying the number and percentage of patients with at least one TEAE using only the most severe TEAE recorded at each level of summarization. The total number of events and number of patients with at least one treatment-emergent infection will also be displayed.

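### SAP Appendix 3 pools herpes zoster with other herpes terms and Pneumocystis pneumonia with Pneumonia, so no AE summary table gives a by-arm count of either infection

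*SAP*

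**What the plan says.** Protocol 7.8.4.2 plans the adverse-event summaries at the level of the coded term: "The following AE summaries will be reported by SOC, PT, and treatment". It mentions no combining of terms.

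SAP Section 13 introduces combined terms, defined in Appendix 3. These "will be summarized in AE tables. Listings will include the PTs as coded without applying the PT combining rule". The section states no exception for serious events or for events of special interest.

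Three groups in Appendix 3 matter here:

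- **Pneumonia:** "Pneumocystis jirovecii pneumonia Pneumonia"
- **Herpes virus infection:** "Herpes simplex Herpes zoster Oral herpes"
- **Tachycardia:** "Sinus tachycardia Supraventricular tachycardia Tachycardia Ventricular tachycardia"

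SAP 13.1.4 makes infection an event of special interest. Section 13.1.4.1 describes its content, including: "New or reactivated viral infections include cytomegalovirus, herpes simplex virus, parvovirus B19, varicella zoster virus, West Nile virus, and hepatitis B and C". The same passage names fungal infection as a class. Protocol 6.5.10.1 has a matching definition.

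**The concern.** Most groups in Appendix 3 join near-synonyms, such as general and site-specific abdominal pain, and tidy the tables without loss. The herpes and pneumonia groups differ, because each joins a distinct infection to commoner terms.

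For a B-cell-depleting drug under biosimilar comparison, infection is where a safety difference would be looked for, and the table by treatment group is where it would be seen. If zoster were more frequent in one arm and oral herpes in the other, the combined row could look balanced. A single Pneumocystis case would appear as one more pneumonia. The by-arm number and percentage that the plan gives for other terms would be missing for these two.

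**Working it through.** No figure in the plan needs reproducing. The check compares passages, followed by a short calculation of what a combined row can reveal.

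**1. Where the rule applies.** SAP Section 13 says combined terms "will be summarized in AE tables", without qualification. SAP 13.1 then lists tables for all treatment-emergent events, serious events, events leading to discontinuation, malignancy, infections and infusion-related reactions. The infection table (13.1.4.1) and the serious-event table (13.1.2) are broken down by SOC and PT, for the safety population and its Extension subset. Both inherit the rule.

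**2. Definition against grouping.**

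| Infection | Special-interest text (SAP 13.1.4.1) | Appendix 3 |
|---|---|---|
| Varicella zoster virus | Named individually | Herpes zoster pooled into Herpes virus infection |
| Herpes simplex virus | Named individually | Herpes simplex and Oral herpes pooled into the same row |
| Pneumocystis | Not named; falls under the class fungal | Pooled into Pneumonia |
| Tuberculosis, cytomegalovirus, parvovirus B19, West Nile virus, hepatitis B and C | Named individually | Not listed; rows kept |

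PML is also absent from Appendix 3. SAP 13.1 declines a separate PML table because its own preferred term will show it among the treatment-emergent events. That reasoning works only for a term that is not combined.

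**3. What a combined row can tell the reader.** Tables count patients, using only the most severe event at each level of summarization. A patient with both oral herpes and zoster counts once in the combined row. A row showing *n* patients in an arm is therefore compatible with anywhere from 0 to *n* patients with zoster.

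Illustration with **assumed** counts and the planned group sizes (149 CT-P10, 212 pooled reference):

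- Zoster, 6 against 1: 6/149 = 4.0% and 1/212 = 0.5%.
- Herpes simplex or oral herpes, 4 against 9: 4/149 = 2.7% and 9/212 = 4.2%.
- Combined row if no patient has both: 6 + 4 = 10 against 1 + 9 = 10, so 10/149 = 6.7% and 10/212 = 4.7%.
- Combined row allowing overlap: between 6 and 10 patients in the CT-P10 arm and between 9 and 10 in the reference arm.

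Given only the row 10 against 10, the zoster difference (CT-P10 minus reference) could lie anywhere from 0/149 − 10/212 = −4.7 percentage points to 10/149 − 0/212 = +6.7 percentage points. These counts show the mechanism and predict nothing.

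**4. What remains available.** "Listings will include the PTs as coded without applying the PT combining rule". SAP 13.1 listings carry SOC, PT, verbatim term, intensity and seriousness, all serious events are listed, and SAP Section 5 sorts listings by treatment group unless otherwise specified. The counts can be recovered by hand.

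**5. The tachycardia group.** Protocol 6.5.10.1 names ventricular fibrillation among infusion-related events. That term is not in Appendix 3. Ventricular tachycardia is not named there.

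**The case against.** The best case for the plan has five parts.

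- **The special-interest text defines a category.** It promises no row per virus. Merging terms within the Infections and infestations SOC leaves the number of patients with any infection unchanged. This stands, but it covers the total only, and the table is also specified by preferred term.
- **The change is documented.** Protocol 7.8 allows departures from its planned analyses if the SAP records them, and Section 13 with Appendix 3 does so. This stands: the combining is not a protocol breach. The SAP gives no reason for any group, however.
- **The information survives.** Listings keep coded and verbatim terms and are sorted by treatment group, so rare terms can be counted. This stands, and it is why the point is modest. A listing still gives no number and percentage by arm.
- **Serious events have their own tables, split by intensity.** These use the same combined terms, so a serious Pneumocystis pneumonia appears as a serious pneumonia. This does not remove the problem.
- **Nothing confirmatory depends on it.** Safety is summarized descriptively, with no similarity criterion tied to a preferred-term row. This stands.

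A reader might go further and infer that the tables hide the trial's named risks generally, or that every treatment-emergent table is affected. The documents do not support that. The other individually named infections and PML keep their rows. Appendix 3 contains no neoplasm terms, so the malignancy table is untouched. The tachycardia group sits in the Cardiac disorders SOC and cannot alter the infection table. A reader might also take ventricular tachycardia for an event the protocol lists; it lists ventricular fibrillation.

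**Conclusion.** The point holds for two infections. Herpes zoster is the stronger case, because the SAP's own definition separates the two viruses that Appendix 3 puts in one row. Pneumocystis pneumonia is supported less directly: outside Appendix 3 the documents do not name it. It enters through the class term fungal, and Protocol 4.1.2 mentions opportunistic infection only as an exclusion. Calling it a fungal opportunistic infection is general medical classification.

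The effect is on reporting. Two by-arm frequencies are missing from every summary table and must be counted from listings. How much this matters depends on how many such events occur, which the documents do not give. No primary endpoint or similarity conclusion is affected. Separating ventricular tachycardia is worthwhile as clinical housekeeping, on the ground that it is a distinct event.

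**What to change.** Either of two edits to the SAP is enough for the infections:

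1. Delete Herpes zoster and Pneumocystis jirovecii pneumonia from Appendix 3, so that each is tabulated under its coded term. The pneumonia group then has one member and can be dropped. The remaining herpes group should be relabelled so that its title no longer suggests it includes zoster.
2. Keep Appendix 3, and add to Section 13 that the infection and treatment-emergent serious-event tables will print the coded-term rows beneath each combined term.

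The first is simpler and also corrects the overall treatment-emergent table. As a lesser addition, remove Ventricular tachycardia from the tachycardia group. The second option alone would show it separately only when serious.

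The cost is an appendix edit and a few extra table rows. No new data, recoding or change in trial conduct is needed, and the near-synonym groups stay as they are.
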